10.6.3 Suspected Unexpected Serious Adverse Reaction (SUSAR)

This is defined as a serious adverse reaction, the nature or severity of which is not consistent with the known study treatment information. A serious event or reaction is not defined as a SUSAR when: 'it is serious but expected' or it does not fit the definition of an SAE, whether expected or not.

10.6.4 Safety Review

At each follow-up visit, subjects will be queried with an open-ended question such as: 'How have you been feeling since your last visit?' Additionally, the study staff will review subject diaries and, if it appears that a potential AE was recorded, study staff will query the subject and determine if an AE occurred.

AEs (whether serious or non-serious) and clinically significant abnormal laboratory test value(s) will be evaluated by the PI and treated and/or followed up for up to one month after end of treatment until the symptoms or value(s) return to normal, or acceptable levels, as judged by the PI.

Where appropriate, medical test(s) and/or examination(s) will be performed to document resolution of event(s). Outcome may be classified as resolved, improved, unchanged, worse, fatal or unknown (lost to follow-up).

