9.6.3 Removal of Subjects from the Study

Subject participation in this trial may be discontinued for any of the following reasons:

1. Occurrence of any medical condition or circumstance that, in the opinion of the Investigator, exposes the subject to substantial risk and/or does not allow the subject to adhere to the requirements of the Protocol.
2. Occurrence of a treatment-emergent adverse event (TEAE) or considerable worsening of an AE that, in the opinion of the investigator in consultation with the Medical Monitor and

Sponsor, represents an unacceptable risk to the subject if he/she continues in the study. The investigator must follow the subject until the AE resolves or satisfactorily stabilizes.

3. Pregnancy.
4. Subject's decision to withdraw.
5. Weight loss of >5% if not dieting or intentionally trying to lose weight and after consultation with the Sponsor, at the Investigator's discretion.
6. C-SSRS indicative of suicidal ideation or a PHQ-8 score ≥ 15 , after consultation with a mental health professional, the Sponsor, and at the Investigator's discretion.
7. Requirement for use of prohibited concomitant medication.
8. Subject's repeated failure to comply with protocol requirements or study related procedures.
9. Termination of the study by the Sponsor, FDA, or other regulatory authorities.

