10.1.8 Adverse Events

Adverse events (AEs) will be collected beginning at informed consent and assessed as follows:

Day 1, Weeks 4, 12, 24, 36, and 52

Any treatment emergent AEs will be followed in the clinic for up to one month at the Investigator's discretion until resolved or otherwise judged as clinically stable.

A psoriasis flare will be considered an AE in this study. For further details on Adverse Events please see [Section 10.6](#).

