10.3 Final Study Visit – End of Study

The final study visit will occur approximately at the end of week 52 of overall involvement in the study. The procedures performed during this visit are as described in [Section 10.1](#) and [Section 10.2](#) and the Schedule of Events for the Week 52 visit ([Section 5](#)). A 7 day scheduling leeway period is allowed for this visit. In addition to the listed procedures to be performed, adverse events will be recorded as reported by the participant or as observed and followed to resolution as necessary (see [Section 10.1.8](#)).

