10.4 Early Termination Visit

If a subject is withdrawn or wishes to exit the study, a termination visit will be scheduled. This visit should include the procedures and assessments that would be performed at the final study visit (End of Study visit; see Section 10.3).

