- If the reaction reoccurs, treatment should be discontinued permanently, and the subject followed until the reaction resolves. Given the excellent local toleration in the Phase 1/2a study, such reactions are possible, but unlikely.

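### Section 10.6.4 caps follow-up of all adverse events, serious ones included, at one month after end of treatment, and does not defer to the open-ended rules in 9.6.3 and 10.8

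*Protocol*

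**What the plan says.** The protocol sets adverse event follow-up in several places.

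- **10.6.4 Safety Review** is the general rule. Its scope is explicit: "AEs (whether serious or non-serious) and clinically significant abnormal laboratory test value(s) will be evaluated by the PI". Such events are to be "treated and/or followed up for up to one month after end of treatment until the symptoms or value(s) return to normal", or reach a level acceptable to the principal investigator. The month runs from end of treatment. No event type is excepted.
- **10.1.8 Adverse Events**, repeated almost word for word in footnote g of the section 5 schedule: "Any treatment emergent AEs will be followed in the clinic for up to one month at the Investigator's discretion until resolved", or until the event is judged clinically stable. Neither place says when the month starts.
- **9.6.3 item 2**, for a subject removed because of a treatment-emergent event or a considerable worsening of one: "The investigator must follow the subject until the AE resolves or satisfactorily stabilizes". There is no time limit.
- **10.8 Treatment Stopping Rules**, for application site reactions: "If the reaction reoccurs, treatment should be discontinued permanently, and the subject followed until the reaction resolves". Again there is no time limit.
- **10.3 Final Study Visit**: "adverse events will be recorded as reported by the participant or as observed and followed to resolution as necessary", with a cross-reference to 10.1.8.
- **10.4 Early Termination Visit** points to 10.3: "This visit should include the procedures and assessments that would be performed at the final study visit".

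**The concern.** This is a long-term safety study whose two primary endpoints are the occurrence of treatment-emergent and of serious adverse events. The general safety section puts a one-month ceiling on follow-up and applies it expressly to serious events. Two other sections require open-ended follow-up for particular events, and nothing in 10.6.4 says that they take precedence. For a serious event that did not lead to removal, no section gives a firm duty beyond one month.

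Two things are at stake. The first is subject safety: a site that relies on 10.6.4 could stop following an unresolved, unstable serious event, or one that led to withdrawal, at one month. The second is the record. Section 10.6.5 requires duration and outcome for each event, and the listing in 11.2.1 shows stop date and outcome. One site could close an event as unchanged or worse at one month while another follows the same kind of event until it resolves.

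**Working it through.** The protocol states no figure to reproduce here. The check is to apply the rules to each type of event that is still open one month after the last dose.

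1. **Non-serious event, drug not stopped for it.** 10.6.4, 10.1.8 and footnote g all give one month. No conflict.
2. **Event already at an acceptable level or clinically stable.** 10.6.4 accepts a level the investigator finds acceptable, 10.1.8 and footnote g accept clinical stability, and 9.6.3 accepts satisfactory stabilization. These end conditions are close, so the rules hardly differ here. Only 10.8 insists on resolution.
3. **Subject removed for a treatment-emergent event, not stable.** End of treatment is about the date of removal. 10.6.4 lets follow-up end about one month later; 9.6.3 item 2 requires it to continue.
4. **Recurrent application site reaction, not resolved.** 10.6.4 allows an end at one month; 10.8 requires follow-up to resolution.
5. **Serious event open at Week 52, subject not removed.** 9.6.3 item 2 does not apply. Only 10.3 points past one month. It does so as necessary, and it refers back to 10.1.8, where the one-month wording stands.
6. **Serious event open when the subject leaves early for another reason.** 10.4 leads to 10.3, so the position is as in case 5.
7. **Event or laboratory abnormality that stops drug without removal from the study.** 10.8 stops treatment for, among other things, a confirmed and drug-related Grade 3 laboratory abnormality, but gives no follow-up period there. 9.6.3 item 2 covers removal only, so 10.6.4 governs.

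Cases 3 and 4 are differences between a general rule and specific rules. Cases 5 to 7 are events for which no specific rule lifts the ceiling.

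**Size.** The protocol gives no event rates, so every percentage below is an assumption. Planned N = 300 (Cohort 1) + 100 (Cohort 2) = 400.

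Group A, removed for a treatment-emergent event (assumed 1% to 5%) and neither resolved nor stable one month after the last dose (assumed 10% to 30% of those):

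- low: 400 × 0.01 × 0.10 = 0.4
- high: 400 × 0.05 × 0.30 = 6

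Group B, serious event without removal (assumed 1% to 5%), ongoing at Week 52 (assumed 10% to 25% of those), and still open about 4 weeks later, near Week 56 (assumed 10% to 30% of those):

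- low: 400 × 0.01 × 0.10 × 0.10 = 0.04
- high: 400 × 0.05 × 0.25 × 0.30 = 1.5

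A + B: 0.44 to 7.5 subjects. Group A, already under the 9.6.3 duty, makes up 0.4/0.44 = 91% of the low total and 6/7.5 = 80% of the high total.

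Cases 6 and 7 are not in these figures; there is no basis in the protocol for sizing them. Case 4 has no separate count either, and 10.8 itself calls such reactions unlikely.

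**The case against.** The strongest reply is that there is no real contradiction. 10.6.4 is the general rule, 9.6.3 item 2 is a mandatory rule for one subset, and 10.8 is a rule for another. A site complies with all three by following those subsets longer, and 10.6.4 does not forbid it. This largely stands: it is the best reading of cases 3 and 4. What remains is that 10.6.4 names serious events, carries no exception, and leaves the site to work out the ranking. The reply does not reach case 5, 6 or 7.

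A second reply is that 10.1.8 and footnote g speak of follow-up in the clinic, which may leave room for contact by phone, and that the acceptable-level and stability conditions end most follow-up properly anyway. Both points stand and narrow the concern. But 10.6.4 has no in-clinic qualifier, and an event that is neither acceptable nor stable at one month still meets the ceiling.

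A third reply is that 10.6.4 is not the only text on serious events, since 10.6.2 commits to regulatory and ICH requirements and to following required procedures. That is correct, so a reader should not infer that serious events are governed by 10.6.4 alone. But 10.6.2 states no follow-up period, so it does not settle the question within the protocol.

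Finally, extending follow-up of serious events goes beyond reconciling 10.6.4 with 9.6.3 and 10.8. This is fair: that part is a recommendation on design. It is justified by the study's safety purpose and its small cost.

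**Conclusion.** The point holds in limited form. 10.6.4 sets a one-month ceiling that expressly covers serious events and does not defer to two sections with no time limit. A serious event in a subject not removed for it has only a soft provision that leads back to the one-month wording. This should be corrected.

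Two stronger inferences are not supported. A reader might conclude that all follow-up simply stops at one month, or that the sections cannot be reconciled. The end conditions and the specific-rule reading show otherwise, and the effect is confined to events that are neither resolved, acceptable nor stable at one month. A reader might also conclude that the primary endpoints are compromised. They are not: 10.6.1 collects events from consent through study completion, so the counts of treatment-emergent and serious events stay the same whatever the length of follow-up. What can vary between sites is outcome, duration and stop date.

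Under the assumed rates, about 0.4 to 7.5 of 400 planned subjects fall in the two groups that can be sized. Only 0.04 to 1.5 of them would come under a new duty. Serious events open at early exit, and events that stop drug without removal, would add to that by an amount the protocol gives no means to estimate.

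**What to change.** Amend 10.6.4 to say:

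- serious adverse events, and adverse events or laboratory abnormalities that lead to discontinuation of drug or removal from the study, are followed until resolution or satisfactory stabilization, by phone if needed;
- recurrent application site reactions are followed to resolution, as in 10.8;
- all other adverse events keep the limit of one month after end of treatment.

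Align 10.1.8, 10.3 and footnote g of the section 5 schedule with this wording, so that the cross-reference from 10.3 no longer leads back to an unqualified one-month limit.

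The cost is a wording change in four places and a few follow-up contacts beyond one month. For removals due to a treatment-emergent event, those contacts are already required by 9.6.3. The new contacts are for serious events open at Week 52 or at early exit, and for events or laboratory abnormalities that stop drug without removal. No scheduled visit, sample size or analysis changes.

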10.6.5 Adverse Event Reporting

The PI will review each event and assess its relationship to drug treatment (unrelated, unlikely, possibly, probably, likely). Each sign or symptom reported will be graded on the NIH NCI CTCAE toxicity grading scale 5-point severity scale (Grade 1, 2, 3, 4 and 5). The date and time of onset, time relationship to drug dosing, duration, and outcome (resolved, improved, unchanged, worse, fatal, or unknown/lost to follow-up) of each event will be noted.

The relationship of each AE to the study drug will be assessed using the following definitions:

Unrelated	
 The AE must clearly be caused by the subject's clinical state, or the study procedure/conditions. Definitely not related to drug. Temporal sequence of AE onset relative to administration of drug not reasonable. Another obvious cause of an AE.
Unlikely	
 Time sequence is unreasonable. There is another more likely cause for an AE.
Possibly	
 Corresponds to what is known about the drug. Time sequence is reasonable. Could have been due to another equally, likely cause.
Probably	
 Is a known effect of the drug. Time sequence from taking drug is reasonable. Ceases on stopping the drug.

	
 • Cannot be reasonably explained by the known characteristics of the subject's clinical state.
Likely	
 • Is a known effect of the drug (e.g., listed in Physicians' Desk Reference, Compendium of Pharmaceuticals and Specialties, IB). • Time sequence from taking drug is reasonable. • Event stops upon stopping drug, event returns upon restarting drug.

The following CTCAE toxicity grading scale 5-point severity scale definitions for rating maximum severity will be used:

Grade 1	Mild; asymptomatic or mild symptoms; clinical or diagnostic observations only; intervention not indicated.
Grade 2	Moderate; minimal, local or noninvasive intervention indicated; limiting age-appropriate instrumental activities of daily living.*
Grade 3	Severe or medically significant but not immediately life-threatening; Hospitalization or prolongation of hospitalization indicated; disabling; limiting self-care activities of daily living.** Note: An experience may be severe but may not be serious, e.g., severe headache).
Grade 4	Life-threatening consequences; urgent intervention indicated.
Grade 5	Death related to AE.

Note: A semi-colon indicates 'or' within the description of the grade.

*Instrumental activities of daily living refer to preparing meals, shopping for groceries or clothes, using the telephone, managing money, etc.

**Self-care activities of daily living refer to bathing, dressing and undressing, feeding self, using the toilet, taking medications, and not bedridden.

AEs will be coded using the most current MedDRA® version available at the start of the study (e.g., 21.0 or higher).

10.7 Reporting Pregnancy

During the study, all subjects should be instructed to contact the investigator immediately if they suspect they might be pregnant (e.g., missed or late menstrual period). If pregnancy is confirmed, the subject will be withdrawn from the study and followed until the pregnancy comes to term.

The investigator is responsible for reporting all available pregnancy information on the pregnancy report within 24 hours of becoming aware of the event, although pregnancy itself is not considered an AE. Study treatment must be discontinued immediately in the event of a pregnancy. The subject should be referred to an obstetrician/gynecologist experienced in reproductive toxicity for further evaluation and counseling. Monitoring of the subject should continue until the conclusion of the pregnancy. Follow-up information detailing the outcome of the pregnancy and the health of the newborn should be reported as it becomes available.

Partner pregnancies of a male subject do not need to be reported.

Any pregnancy complication or premature terminations including miscarriage, spontaneous abortion or elective termination of a pregnancy for medical reasons will be reported as an SAE, as described in [Section 10.6.2](#). Should the pregnancy result in a congenital abnormality or birth defect, a separate SAE report must be submitted. Furthermore, all neonatal deaths that occur within 30 days of the birth should be reported as SAEs, without regard to causality. In addition, any infant death that occurs after the 30-day reporting period that the investigator suspects is related to the in-utero exposure to the study treatment should also be reported.

10.8 Treatment Stopping Rules

For subjects that clear (i.e. have an IGA score of 0 (Clear), an I-IGA (if applicable) of 0 (Clear) **and** an mPASI of 0) treatment may be stopped. The subject will be instructed to document in their diary when they resume treatment with study drug if psoriasis returns. If the subject clears between study visits they should be scheduled for an unscheduled visit for the Investigator to confirm the subject has cleared.

Subjects will call the site when psoriasis returns prior to restarting application of study drug.

If a subject has non-cutaneous adverse events of concern, clinically significant laboratory values or any condition that the investigator determines could possibly be related to the study drug, the Investigator should immediately contact the Medical Monitor to discuss if the subject should be discontinued from the study.

Treatment for any individual subject will be discontinued if the subject experiences:

- A serious adverse event (SAE) or a clinically significant non-serious AE which in the opinion of the Principal Investigator or Medical Monitor warrants discontinuation from the study for that subject's well-being.
- A severe (Grade 3) laboratory abnormality (confirmed by repeat sample and considered related to study drug).
 - See [Appendix 2](#) for details.

Dosing of study drug for an individual subject may be suspended for safety concerns other than those described above, at the discretion of the investigator if he/she feels the subject's safety may be threatened.

A subject with a PHQ-8 score of '15' or above should be referred promptly to a mental health care professional and consideration be given to discontinuation from study drug.

A subject that is experiencing suicidal ideation and behavior should be referred immediately to a qualified mental health care provider and consideration given to discontinuation from study drug.

As noted above, study treatment must be discontinued immediately in the event of a female subject's pregnancy.

Treatment should be interrupted:

- If a subject develops an application site reaction with the clinical appearance of an 'irritation reaction', and with a severity of a Dermal Response Score of 5 (erythema, edema and papules) or greater on the scale of Berger and Bowman. Treatment can be interrupted for up to one week and may then be resumed if the reaction has, in the opinion of the Investigator, adequately resolved.

Treatment should be discontinued:

- If the reaction reoccurs, treatment should be discontinued permanently, and the subject followed until the reaction resolves. Given the excellent local toleration in the Phase 1/2a study, such reactions are possible, but unlikely.

11 DATA ANALYSIS

Data will be handled and processed according to the Contract Research Organization's Standard Operating Procedures, which are written based on the principles of GCP.

11.1 Statistical Methods

The methodology presented below is a summary of the more detailed analysis plan that will be presented in the Statistical Analysis Plan (SAP). The SAP will be finalized before the database is locked and unblinded. Any changes to the methods described in the final SAP will be described and justified in the clinical study report.

All statistical processing will be performed using SAS[®] (Version 9.4) unless otherwise stated. No interim efficacy analyses are planned.

Descriptive statistics will be used to provide an overview of the safety and efficacy results. For categorical parameters, the number and percentage of subjects in each category will be presented. The denominator for percentage will be based on the number of subjects appropriate for the purpose of analysis. For continuous parameters, descriptive statistics will include n (number of subjects), mean, standard deviation (SD), median, minimum, and maximum.

Missing efficacy and/or safety data will remain missing and will not be estimated.

11.1.1 Baseline Definition

Cohort 1 baseline value for each parameter will be defined as the last observation prior to first dose of ARQ-151 cream 0.3% or ARQ-151 cream 0.15%. For subjects receiving either active study drug in ARQ-151-201, the baseline values from ARQ-151-201 will be considered the baseline values for calculations in ARQ-151-202. For subjects receiving Vehicle in ARQ-151-201, baseline values will most commonly be from the Week 12/study exit visit of ARQ-151-201. If subjects choose to enroll in this study, study procedures will not be repeated; study sites will carry over the information from the ARQ-151-201 study (Week 12 visit) to the Day 1 visit for this study. Baseline values for IGA, however, will be taken from Day 1 of Study ARQ-151-201 for all subjects.

Cohort 2 baseline value for each parameter will be collected on Day 1.

11.1.2 Determination of Sample Size

A sample size of approximately 300 subjects is planned for Cohort 1 and up to approximately 100 subjects in Cohort 2 is planned for the study. This sample size will provide a sufficient population size to evaluate the long-term safety of ARQ-151 cream 0.3% at 52 weeks.

11.1.3 Subjects to Analyze

All analyses will be performed using the Safety Population which includes all subjects who are enrolled and received at least one confirmed dose of ARQ-151 cream 0.15% or ARQ-151 cream 0.3% study medication either in the Phase 2b Study (ARQ-151-201) or this extension study (ARQ-151-202). The number of patients included in the Safety Population will be summarized.

11.1.4 Interim Analysis

No interim efficacy analyses are planned.

11.1.5 Background and Demographic Characteristics

Descriptive statistics will be used to summarize demographic characteristics (age, sex, and race) and background characteristics for the enrolled subjects. Past/coexistent medical history information and physical examination observations and vital signs information for all subjects will be presented in a by-subject listing.

11.1.6 Study Medication Compliance

The number of study drug applications by each subject based on diary data will be summarized using summary statistics (mean, standard deviation [SD], median, minimum, and maximum), and categorically.

The amount of study medication used by each subject based on tube weight will be summarized using summary statistics (mean, SD, median, minimum, and maximum), and categorically.

